The Data Safety and Monitoring plan for this study will include a Data Safety and Monitoring Board (DSMB). The DSMB will consist of [name] endocrinologist and diabetes specialist, [name] an adult cardiologist, and [name] RN, BSN, CDE. All members of the DSMB disclose no conflict of interest related to the proposed trial. The DSMB will have a scheduled meeting twice a year or after an additional 30% of the total anticipated subjects have been enrolled to monitor the study progress and integrity to examine the patient laboratory results, and to assess adverse events (see below) to ensure that patients are not exposed to unnecessary risk during the study.

During screening and baseline evaluation and during the study, serum and urinary calcium levels will be monitored to assess for possible risk of hypercalcemia associated with vitamin D intoxication. Serum calcium >10.5 mg/dl or urinary calcium: creatinine ratio >1.0 at screening or during the course of the study would necessitate that the subject be ineligible for randomization or be withdrawn from the study. This decision will be made by the PI or his designated staff without regard to knowledge of treatment group assignment. In addition, 25(OH) vitamin D levels will be provided to a member of the DSMB to review and alert the PI to any subject who should be withdrawn from the study because of a 25-OHD >200ng/ml during the study (57).

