
The DSMB will be informed of all Serious Adverse Events (SAEs). An SAE will be defined as an event which results in any of the following outcomes: death, life-threatening event, persistent or significant disability, inpatient hospitalization or prolongation of an existing hospitalization, or congenital anomaly. In addition, any symptomatic patients with stroke, intracranial bleeding, heart attack, heart failure, symptomatic hypocalcemia/ hypercalcemia, or increased urinary calcium/creatinine ratio >1.0 that is unresponsive to fluid therapy (at least six to eight glasses of water per day for 5 days) will be considered to be an SAE and withdraw. The PI will determine if the SAE is causally related to the study without regard to knowledge of treatment group assignment. Any patient with an SAE which is determined by the PI to be possibly or probably related to the study intervention will be withdrawn from the study. All SAEs will be reviewed by the DSMB to confirm the PI's assessment of causality and will be reported to the Institutional Review Board (IRB) and CARS Research Subject Advocate. Symptomatic subjects who develop sustained severe symptomatic hypertension during the study defined as SBP >160 mmHg and/or DBP >100 mmHg by office BP measurements (confirmed by ABPM) will be evaluated by [name] and/or [name] and he/she will determine if patient will be withdrawn by determine the clinical risk to develop hypertensive complications. The physician will also determine if there is a clear triggering factor that is causing the increase in blood pressure and if it is easy to resolve it before patient is dropped from the study. The participant's primary care doctor will be notified and antihypertensive therapy will be started as per their recommendation. If patients do not have a primary care doctor, antihypertensive therapy will be started and they will be referred to a medical provider for further management

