that is covered by their insurance. The initial goal is to reduce blood pressure to 160/ 110 mm Hg over several days, we will follow these patients closely until this ambulatory BP is achieved. Patients with increased urinary calcium/creatinine ratio >1.0 that are unresponsive to oral fluid therapy, will be evaluated in the CRU to determine whether IV fluid therapy is required. We will follow this patients until they achieve urinary calcium/creatinine ratio <1.0. Patients with asymptomatic hypocalcemia that are unresponsive to increased PO Calcium intake we will supervise calcium intake by clinic visits and follow until plasma calcium levels return to normal. If the patient becomes symptomatic and requires a hospitalization, the patient will be withdrawn from the study. Patients that have completed at least 8 weeks in the study and are withdrawn for medical reasons, will continue to be evaluated every 4 weeks for BP monitoring, plasma calcium levels and urinary calcium and creatinine ratio until completing 16weeks from the initiation of the trial. At 16 weeks AMBP monitoring and FMD and macrophages will be obtained.

Summary reports of all Adverse Events (non-serious AEs and SAEs) will be provided to the DSMB before each scheduled meeting and at least every 4 months. If the PI or the DSMB determine that there are an unacceptable number of AEs and/or SAEs reported, the PI may request that the DSMB review (or the DSMB may independently decide to review) the events by unmasked treatment group. If treatment-emergent AEs or SAEs are occurring at an unacceptable rate, the DSMB may recommend to the PI that the study be halted or that the protocol be modified.

References

3. Killilea T. Long-term consequences of type 2 diabetes mellitus: economic impact on society and managed care. *Am J Manag Care* 8:S441-9, 2002
4. Tight blood pressure control and risk of macrovascular and microvascular complications in type 2 diabetes: UKPDS 38. UK Prospective Diabetes Study Group. *Bmj* 317:703-713, 1998

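### The only stated route to adverse events by arm is a prior, undefined judgement that the number is unacceptable; routine A/B tables for the DSMB would be a cheap improvement

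*Combined protocol and SAP*

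**What the plan says.** All of this is in the Data and Safety Monitoring Plan of the combined protocol and SAP, unless another section is named.

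- **Routine reports.** "Summary reports of all Adverse Events (non-serious AEs and SAEs) will be provided to the DSMB before each scheduled meeting". The longest interval allowed between them is 4 months. No layout is given, and no split by arm, coded or not, is mentioned.
- **Meetings.** "The DSMB will have a scheduled meeting twice a year or after an additional 30% of the total anticipated subjects have been enrolled". Examining patient laboratory results is among the board's tasks.
- **Review by arm.** The condition is "If the PI or the DSMB determine that there are an unacceptable number of AEs and/or SAEs reported"; then "the PI may request that the DSMB review (or the DSMB may independently decide to review) the events by unmasked treatment group".
- **Halting.** "If treatment-emergent AEs or SAEs are occurring at an unacceptable rate, the DSMB may recommend to the PI that the study be halted". A protocol modification is the stated alternative. Neither the number nor the rate is defined.
- **SAEs.** "The PI will determine if the SAE is causally related to the study without regard to knowledge of treatment group assignment". "All SAEs will be reviewed by the DSMB" to confirm that causality assessment.
- **Individual limits.** Serum calcium above 10.5 mg/dl or a urinary calcium:creatinine ratio above 1.0 leads to ineligibility or withdrawal. Separately, "25(OH) vitamin D levels will be provided to a member of the DSMB to review and alert the PI" to any subject above 200 ng/ml.
- **Interim analysis.** It takes place at 60 of 120 enrolled, concerns efficacy and focuses on the primary endpoint.
- **Background treatment** (Protocol section). Both arms receive calcium carbonate 1.2 g/day.

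**The concern.** The board is there to see that patients are not exposed to unnecessary risk. For events that also occur without the study drug, the relevant evidence is the difference between the arms. The plan provides for that comparison, but only after someone has found the number of events unacceptable.

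That judgement has little to rest on. No expected rate is stated. Because placebo patients also take calcium, some calcium-related events in the placebo arm are plausible, so a given total could be background or could be an excess in the vitamin D arm. The trial has the right comparator in its placebo arm, but the plan does not routinely show it to the board. At stake is later recognition of a moderate excess in one arm, mainly of events that are too mild, or of the wrong kind, to trigger the individual rules.

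**Working it through.** **Reading the text.** The PI's option and the board's option both sit inside the same conditional sentence. Review by arm as a separate, triggered step would be redundant if the routine summaries were already split, so I infer that they are not. No other provision fills the gap: the interim analysis is about efficacy, SAE review is case by case, and the calcium and 25(OH)D limits act on one patient at a time.

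**Arm sizes.** The Statistics section gives 120 recruited, 20% dropout and 48 per group. Check: 120 × (1 − 0.20) / 2 = 48, which implies 1:1 allocation and 60 per arm at full enrolment. Meetings after each additional 30% come at 0.30 × 120 = 36 enrolled (18 per arm) and at 72 enrolled (36 per arm).

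**Event rates.** The documents give none. All rates below are assumptions, placebo first.

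**What a total can show.** With arms of equal size, the expected overall rate is (p0 + p1)/2, so an excess in one arm is halved. For 60 per arm, the table gives the probability that the total out of 120 is high by a one-sided exact binomial test at 0.05, for different presumed background rates. The last column is one-sided Fisher power at 0.05 for the comparison by arm, which needs no presumed rate.

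| Assumed rates | Expected by arm | Expected total | Total looks high, by presumed background | By arm |
|---|---|---|---|---|
| 5% vs 15% | 3 vs 9 | 12/120 = 10% | 0.67 (5%); 0.03 (10%) | 0.48 |
| 5% vs 20% | 3 vs 12 | 15/120 = 12.5% | 0.90 (5%); 0.54 (7.5%); 0.16 (10%); 0.04 (12.5%) | 0.76 |
| 10% vs 30% | 6 vs 18 | 24/120 = 20% | 0.91 (10%); 0.36 (15%); 0.04 (20%) | 0.83 |

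In each row, a total judged against the correct placebo rate is more sensitive than the comparison by arm. It loses that advantage once the presumed background is a few points too high. The weakness is therefore the missing reference rate rather than pooling as such.

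**What tables by arm would show over time**, assuming 5% vs 20%. Counts are rounded to whole events.

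| Per arm | Approximate counts | Two-sided Fisher p at those counts | Two-sided Fisher power at 0.05 |
|---|---|---|---|
| 18 | 1 vs 4 | 0.34 | 0.13 |
| 36 | 2 vs 7 | 0.15 | 0.34 |
| 60 | 3 vs 12 | 0.025 | 0.63 |

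These figures treat every enrolled patient as fully followed, so they flatter the early meetings.

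**The case against.** The plan's arrangement is a recognised policy: stay masked unless concerned. It contradicts nothing else in the document. Four further points have weight.

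- **Access.** A reader might infer that the PI controls access to data by arm. The text does not support that. The board may start the review itself, and since the trigger is undefined it could do so on modest concern. What stands is that the board's own option depends on the same judgement, with no stated rate to inform it.
- **Pooling.** A reader might take pooled totals to be mandated. The plan never says so, and the board also examines laboratory results.
- **Calcium events.** A reader might conclude that calcium toxicity would go unseen. It would not. The Protocol section has calcium and the urinary ratio checked every 2 weeks for six weeks and then monthly, with individual withdrawal limits. Symptomatic hypercalcemia, or a raised ratio unresponsive to fluids, counts as an SAE. The 25(OH)D levels may also suggest the arm to one board member, although the documents give no expected on-treatment levels. These measures protect individuals but do not compare rates between arms.
- **Detection.** A reader might take p = 0.025 for 3 vs 12 as what tables by arm would deliver. That figure rests on assumed rates at full enrolment; the earlier meetings would usually show nothing significant. Nor is a total always uninformative: against a known 5% background, 15/120 gives a one-sided p of 0.001, though against 10% it gives 0.22.

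**Conclusion.** The point holds as a modest one. The only stated route to adverse events by arm runs through an undefined judgement, and no routine comparison of the arms for safety is described. With calcium in both arms and no expected rate, a moderate excess in one arm could go unnoticed for longer than it need.

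The size cannot be fixed from the documents. Under the assumed rates at 60 per arm, the chance that a total raises concern runs from 0.03 to 0.91, depending mainly on the background the board presumes. The conclusion rests on 1:1 allocation (implied by 48 per group), on the inference that routine summaries are not split, and on there being some placebo-arm events. It does not mean that patients are unprotected, that the PI can block review, or that the efficacy analysis is affected.

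**What to change.** Before each scheduled meeting, send the DSMB a closed report with adverse events and serum and urinary calcium tabulated by coded arm (A/B). It can be prepared by whoever holds the allocation code for the planned interim analysis, or by the pharmacy, which carries out the assignment. Keep the reports that investigators see masked. Remove the unacceptable-number condition for review by arm. State that the tables inform the board's judgement and are not a formal test.

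Cost: one additional closed report per meeting and a named preparer outside the study team, whom the documents do not yet identify. The plan already provides for review by arm and for an interim comparison of efficacy, so splitting the data needs no new procedure. Sample size, endpoints, visits and treatment do not change. There are two downsides: board members may infer which arm is which, and early counts will be too small to interpret firmly.
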